ISSSTE

Medical Unit: Subdirección de Enseñanza e Investigación C.M.N. "November 20"

IDENTIFICATION OF BIOMARKERS DERIVED FROM ADIPOSE TISSUE WITH POTENTIAL UTILITY IN THE DIAGNOSIS AND PROGNOSIS OF CARDIOVASCULAR RISK OF OBESE PATIENT

**DR. [name], DR. [name], DRA. [name], DR. [name] and DR. [name].**

Background

Obesity is a nutritional disorder that is considered a risk factor for several metabolic abnormalities, such as insulin resistance, Diabetes Mellitus type 2 (DM2), NAFLD, endothelial dysfunction, cardiovascular risk and is associated with high morbidity and mortality.

According to the panel of experts from the National Heart and Lung Institute of the United States, "obesity is a chronic disease that results from the interaction of the genotype and the environment." In 1997, the World Health Organization defined obesity as "an excess of fat that accumulates in such an amount that health can be adversely affected." In Mexico, obesity represents a priority problem for public health, since its high frequency places the country in second place of prevalence worldwide.

A scale to classify obesity is the body mass index (BMI), in which the obese subject is one with a $\text{BMI} \geq 30\text{kg} / \text{m}^2$ and subdivided into 3 classes (Table 1).

Table 1. Body Weight Classification According to the BMI in Adults

	BMI
Normal	18.5-24.9 kg / m ²
Obese Grade 1	30-34.9 kg / m ²
Obese Grade 2	35.0 -39.9 kg / m ²
Obese Grade 3	≥ 40 kg / m ²

Morbid Obesity

Morbid obesity refers to an extreme degree of obesity, which affects basic physiological functions and is related to specific risks (Table 2). It has been estimated that a morbid obese man reduces his life expectancy by up to 22% compared to an individual of normal weight.

Table 2. Impact on the long-term health of morbid obesity

Decreased life expectancy
Dyslipidemia
Decrease in the quality of life of economic and social opportunities
Obstructive sleep apnea
Cardiovascular diseases
Gastroesophageal reflux disease
DM2
Cancer
Depression
Osteoarthritis
Hypertension
Kidney failure

Bariatric Surgery

Bariatric surgery not only induces weight loss, but also significantly improves the covariabilities associated with morbid obesity in those patients accepted. Clinical trials and observational studies have shown that bariatric surgery can prolong survival in patients with extreme obesity. In fact, the National Institutes of Health of the United States recommend bariatric surgery that should be presented with $BMI > 40 \text{ kg} / \text{m}^2$ or $> 35 \text{ kg} / \text{m}^2$ concomitant related to obesity.

Surgeries to reduce food intake reduce the amount of oral intake through a bag that limits the passage of food. It has also been proposed that a) it would induce a sense of emergence or suppression of appetite as a mechanism in weight loss; b) compress the vagus nerve; c) decreased the secretion of gastrointestinal hormones, such as ghrelin or peptide YY. The surgeries that are included in this type are the adjustable gastric band and sleeve gastrectomy.

Hybrid procedures are represented by the gastric Roux-en-Y derivation (DYRG), which involves reducing the size of the stomach by 15 ml by resecting the upper stomach portion and anastomosing it to the small intestine. The stomach remains viable but the

food is derived from the small intestine and the remaining stomach has a lower capacity; the duodenum does not absorb the macronutrients responsible for post-prandial hormonal responses.

Appetite reduction can be partially explained by the YY principle and the glucagon-like principle¹⁻³. The duodenum bypass also contributes to decrease the absorption of iron and calcium, requiring its supplementation⁴. The biliopancreatic diversion (BPD) involves the resection of the upper 2/3 of the stomach, leaving a stomach capacity of 250 ml, disconnecting half of the jejunum and ileum from the alimentary tract and reconnecting it to the terminal ileum. With the delay in the action of the digestive enzymes within the alimentary tract, most of the fat and a significant fraction of the proteins is excreted as a result of the decrease in its ingestion. There is a dramatic loss in weight, but certain micronutrients are not absorbed, so supplements are required. There is a modification of DBP, called "switch" DBP, which consists of a sleeve gastrectomy with a less dramatic intestinal derivation. The difference lies in the preservation of the pylorus, which leads to fewer complications.

- H1 Metabolic phenotypes based on basic mechanisms of adipose tissue are associated to the cardiovascular risk modification after bariatric surgery.
- H0. Metabolic phenotypes based on basic mechanisms of adipose tissue are NOT associated to the cardiovascular risk modification after bariatric surgery.

GENERAL OBJETIVE

To evaluate the association of the cardiovascular benefit of the obese patient after bariatric surgery with the basic mechanisms of adipose tissue (metabolic profile)

SPECIFIC OBJECTIVES

- Characterize the basal (pre-surgical) metabolic profile of adipose tissue.
- Evaluate post-surgical modification of cardiovascular prognosis
- Determine the association of the cardiovascular prognosis modification (risk subgroups) with the basal metabolic profile.

DESIGN

This is an OBSERVATIONAL study, of a prospective cohort follow-up. We will study morbidly obese patients who undergo bariatric surgery (this is not a proposal of the present protocol, it is routinely done as a treatment for morbid obesity in the CMN "20 de Noviembre", ISSSTE, and it would also be carried out although the patient does not participate in this study). It was considered that the independent variable is the change in cardiovascular risk after bariatric surgery and the dependent variable is the basal metabolic profile of adipose tissue. This order of variables was decided by methodological strategy, since it will be more convenient to determine and stratify based on the change in cardiovascular risk, than based on the basal metabolic profile of adipose tissue.

$$n = \frac{(Z^{\alpha/2})^2 (p(1-p))}{d^2}$$

where:

n = sample size.

$Z^{\alpha/2} = Z$

value of the alpha error with a confidence of 95%, assigning alpha = 0.05

p =

Expected population prevalence for the event under study (according to previous reports).

d

=difference between the expected population prevalence value and the acceptable error. Considering the average difference in the modification of the basic mechanisms in adipose tissue associated with metabolic risk in similar studies

$$\begin{array}{ll}
 (1.96)^2 (0.20 (1-0.20)) & 0.614 \\
 n = \frac{\text{_____}}{(0.13)^2} & n = \frac{\text{_____}}{0.0169} = 36.3
 \end{array}$$

Additionally, for reasons of comparison and standardization of results, a C group would be considered: 10 non-obese patients undergoing non-bariatric surgery.

Definition of the observation units.

Patients with morbid obesity subjected to bariatric surgery, with significant modification of cardiovascular risk in the postoperative period.

Definition of the control group

Due to the observational design of the before-after evaluation (of bariatric surgery), the morbidly obese patient in the pre-surgical baseline is his own reference ("control") for the postoperative period. It is also considered non-obese subjects subjected to abdominal surgery eg. Hernioplasty, fundoplication etc. to know the "normal" metabolic profile of adipose tissue.

Inclusion criteria

- Men and women.
- Over 18 years.
- With morbid obesity and candidates for bariatric surgery, under the routine of the treating service.
- Signature of acceptance of your participation, through informed consent.

Exclusion criteria.

- Medication with potential effect on fatty tissue or cardiovascular risk in the last month.
- Serious infections in the last month.
- Clinically unstable conditions.

Elimination criteria.

- Desire not to continue in the study
- Samples or insufficient information for an adequate analysis.

Definition of variables and units of measurement.

Definition of variables and units of measurement.			
Variable	Dependent / Independent	Type	Units of measurement
Total body fat, visceral and subcutaneous	Dependent	Discontinuous Quantitative	Percentage
Serum markers of inflammation PCR and IL-6	Dependent	Quantitative continuous	µUI / dL
Serum adipokines: leptin and adiponectin	Dependent	Quantitative continuous	µUI / dL
Differentiation and hypertrophy of adipocytes and angiogenesis	Dependent	Qualitative dichotomous	Present or absent
Pro-inflammatory markers at tissue level	Dependent	Qualitative dichotomous	Present or absent
Oxidative stress and tissue endoplasmic reticulum	Dependent	Qualitative dichotomous	Present or absent
Insulin sensitivity	Dependent	Qualitative dichotomous	Sensitive or not sensitive
HOMA	Dependent	Qualitative dichotomous	Higher or lower than 15
Prognostic scales mortality due to independent cardiovascular cause	Independent	Quantitative discontinuous	Own rating
Flow mediated dilatation	Independent	Quantitative discontinuous	Percentage
Carotid intima media thickness	Independent	Quantitative discontinuous	Millimeters

Selection of sources, methods, techniques and procedures for collecting information

With the acceptance of the Institutional Ethics, Research and Biosafety Committees, patients will be invited and included according to the selection criteria.

Prior signature of informed consent, will include patients with morbid obesity, candidates for bariatric surgery and without additional modifiers of adipose tissue metabolism. Patients will be chosen in accordance with the criteria of the Bariatric Surgery Service, without modifying the routine procedures performed in this service.

At the same time, a group of non-obese patients (obesity comparison group) scheduled and undergoing non-bariatric abdominal surgery (hernioplasty, cholecystectomy, appendectomy, etc.) will be included. In all groups, total body fat, subcutaneous and visceral fat will be determined non-invasively by computed tomography, with the support of the Department of Imaging ([name] and [name]) as described below:

TOMOGRAPHIC MEASUREMENT OF SUBCUTANEOUS AND VISCERAL GREASE

Subcutaneous fat:

The thickness of adipose tissue will be measured, in the abdominal thickest site, at the level of the umbilical scar, with references from the skin to the muscular layer, either in vertical measurement (antero-posterior) or in lateral measurement.

Visceral fat:

Epicardial fat: The thickness of the adipose tissue will be measured epicardial level, in the thickest site.

Preperitoneal fat:

The thickness of adipose tissue will be measured, level of the umbilical scar; from the muscular layer (vertical measurement or ant-post) to the first visceral structure.

Perirenal fat:

The thickness of adipose tissue will be measured perirenal, in the thickest site.

During the surgical act, a sample of 1-2 cubic cm of visceral and subcutaneous adipose tissue will be taken, in all groups, considering all aspects of patient Ethics and Biosafety described in the respective sections of this project. In patients with laboratorial evidence and image of progression to NAFLD, a sample of 1-2 cubic cm of liver tissue will be taken, in accordance with international guidelines for diagnosis and treatment, and with the study protocol established by the service. It will be guaranteed that the taking of biopsies will not affect the course of the surgery. The biological samples acquired will be properly identified, contained and stored for a maximum period of 1 year. Analysis and determinations will be made according to good laboratory practices. Subsequently, they will be treated and disposed of in appropriate bags for disposal. To comply with the provisions of section 6 of NOM-087-ECOL-SSA1-2002 Biological-Infectious Waste.

To study the characteristics of each metabolic profile, the following variables will be analyzed:

- a) Adipose tissue (visceral and subcutaneous) where the degree of differentiation and hypertrophy of adipocytes and angiogenesis will be determined by morphometric methods of histopathology; as well as markers of inflammation, oxidative stress, endoplasmic reticulum stress and adipose tissue dysfunction through immunohistochemistry and in vitro tests on isolated adipocytes.
- b) Liver tissue the degree of steatosis, steatohepatitis and fibrogenesis, considered as clinical progression of metabolic damage, will be determined.
- c) Serum level, inflammation markers (TNFa, CRP and IL-6) and adipokines (leptin, adiponectin, resistin) will be determined by ELISA.

Finally, in all groups, follow-up variables related to post-surgical modification of cardiovascular risk will be determined; through:

Prognostic scales of cardiovascular mortality: They will be determined by Drs. [name] and [name], based on probability calculation with variables such as age, gender, co-morbidities, etc. using Framingham or SCORE scales. Place: Clinical Research Division, CMN "November 20", ISSSTE.

Determination of serum markers of endothelial dysfunction and ankle / arm index. They will be determined by [name] [name] and associated researchers, using commercially available ELISA kits and direct determination of systolic pressure in the ankle and arm, with the help of Doppler scan type Doptone, respectively. Place: Biomedical Research Laboratory and Clinical Research Division, CMN "November 20", ISSSTE.

Determination of subclinical atherogenesis (thickness of the carotid intima media). It will be determined by the Department of Imaging, with the support of [name]. The Doppler transducer will be placed in the neck and the common carotid artery will be located, then the thickness of the intimal vascular mean will be determined 1 cm from the carotid bifurcation. The determination will be made by two observers to estimate the inter-observer correlation. Place: Department of Imaging, CMN "November 20", ISSSTE.

The determination of these variables of cardiovascular risk modification will be determined basally and periodically at 3, 6 and 9 months after bariatric surgery, in all groups.

Definition of the processing plan and presentation of the information

Data analysis will be done through descriptive statistics applied to demographic variables, and inferential statistics, which will include difference of averages, correlation, strength of association and relative risk, as well as multivariate logistic regression analysis to evaluate independent associations. With the variables most associated with the modification of cardiovascular risk, a metabolic profile will be established as a predictive model of the greatest cardiovascular benefit after bariatric surgery. Statistical significance will be considered with $p < 0.05$

ETHICAL CONSIDERATIONS

This study is considered as minimal risk. Bariatric surgery (this procedure is not a proposal of the present protocol, it is routinely done as a treatment for morbid obesity in the CMN "20 de Noviembre", ISSSTE and would also be done if the patient does not participate in the study) will be performed according to the routine procedures of the Department of Bariatric Surgery. The project complies with the guidelines and recommendation of the Declaration of Helsinki. The protocol will be submitted to the Ethics and Institutional Research Committee. All patients will be asked to read and sign informed consent.

BIOSECURITY CONSIDERATIONS.

Bariatric surgery procedures are not part of this investigation. In any case, it is emphasized that this project does not alter the surgical procedure and routine biosecurity measures, which are based on the best clinical practice and international recommendations (Neff KJ, le Roux CW, Bariatric surgery: a best practice article. *Pathol* 2013; 66: 90-8). Sampling during surgery will be done in accordance with the Regulation of the General Health Law on Health Research, respecting aspects of taking the appropriate measures to avoid any risk or damage to research subjects (includes adequate preoperative assessment). , biosecurity measures typical of an operating room and sampling by an experienced surgeon). In any case, the privacy of the individual subject of the investigation will be protected, and it will be sought to limit the likelihood that the subject will suffer any harm as a result of the study.

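### The plan makes baseline markers the dependent variable but promises a model that predicts benefit, and its logistic regression has no defined outcome

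*Combined protocol and SAP*

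**What the plan says.** Under DESIGN the protocol states that "the independent variable is the change in cardiovascular risk after bariatric surgery and the dependent variable is the basal metabolic profile of adipose tissue". It says this order was chosen deliberately, because "it will be more convenient to determine and stratify based on the change in cardiovascular risk".

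The table under Definition of variables and units of measurement applies the same roles throughout. The eight fat, serum, tissue and insulin rows are labelled Dependent. The three cardiovascular rows (prognostic scales, flow-mediated dilatation, carotid intima-media thickness) are labelled Independent. Five rows are dichotomous, for example "Pro-inflammatory markers at tissue level", and all five are among the Dependent rows. The three cardiovascular rows are quantitative.

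The analysis section (Definition of the processing plan and presentation of the information) plans "multivariate logistic regression analysis to evaluate independent associations" and does not say what is being regressed. It then says that "a metabolic profile will be established as a predictive model of the greatest cardiovascular benefit after bariatric surgery". The inputs to that model are described only by the phrase "With the variables most associated with the modification of cardiovascular risk".

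Two other places hint at a grouping of patients by outcome. The third specific objective reads "Determine the association of the cardiovascular prognosis modification (risk subgroups) with the basal metabolic profile", and the observation unit is a patient "with significant modification of cardiovascular risk in the postoperative period". Neither gives a scale, cut-off, number of groups or visit. The cardiovascular measures are taken at baseline and at 3, 6 and 9 months.

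**The concern.** A model that predicts benefit has benefit as its outcome and the markers as predictors. The Design section and the variables table assign the opposite roles, and nothing in the document reconciles them.

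The variable types sharpen the conflict. Logistic regression needs a categorical outcome, usually binary, and as tabled the only binary candidates are the markers. An analyst who followed the table would fit the presence of a baseline marker as a function of a risk change measured 3 to 9 months later. That estimates how often a marker is present given the risk change. The promised result is how likely benefit is given the markers.

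Because no regression outcome is named, the model direction, the risk measure, the visit and any benefit cut-off could all be settled after the data are seen.

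**Working it through.** **1. Sample size, for context.** The plan's formula with p = 0.20 and d = 0.13 gives 1.96² × 0.20 × 0.80 / 0.13² = 0.6147 / 0.0169 = 36.4, against the plan's 36.3. The figure reproduces. The point does not depend on it, but it fixes the scale at about 36 patients.

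**2. Table count.**

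| Label | Rows | Quantitative | Dichotomous |
|---|---|---|---|
| Dependent (fat, serum, tissue, insulin) | 8 | 3 | 5 |
| Independent (cardiovascular) | 3 | 3 | 0 |

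No row is a binary benefit variable.

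**3. The two directions answer different questions.** The documents give no marker frequencies or benefit rates, so these are assumptions. Let a marker be present in 60% of patients with benefit and 30% without, and let r be the benefit rate. The stated direction returns 0.60 and 0.30 for any r. The promised quantity is

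P(benefit | marker) = 0.6r / (0.6r + 0.3(1 − r)).

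- r = 0.20: 0.12 / 0.36 = 0.33
- r = 0.30: 0.18 / 0.39 = 0.46
- r = 0.50: 0.30 / 0.45 = 0.67

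**4. A profile also needs the joint distribution of the markers.** Take two such markers with within-group correlation φ. Then P(both | benefit) = 0.36 + 0.24φ and P(both | no benefit) = 0.09 + 0.21φ. At r = 0.30, the probability of benefit when both are present is:

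- φ = 0: 0.108 / (0.108 + 0.063) = 0.63
- φ = 0.5: 0.144 / (0.144 + 0.1365) = 0.51

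In the stated direction the five dichotomous rows have 2⁵ = 32 joint combinations to describe. A main-effects logistic model of benefit on the same five has six parameters.

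**5. Does the reversal inflate false positives?** No. In linear regression, the test of marker B adjusted for marker A is the same whether B or the risk change is the outcome. In 10,000 simulated studies per setting (n = 36, B null given A), both directions flagged B in 4.93%, 4.78% and 4.82% of studies. The three settings had correlations of A with the change and of A with B of (0.3, 0.2), (0.4, 0.4) and (0.5, 0.6).

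**6. Choices left open.** Three tabled risk measures × three follow-up visits = 9 candidate outcomes. Adding the ankle/arm index and the serum endothelial markers, which appear only in the procedures section, gives (3 + 2) × 3 = 15. Both counts are low: the procedures also leave Framingham or SCORE open, and any cut-off adds more.

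**7. How many markers the corrected model can carry.** In linear regression, k pure-noise predictors in n patients have expected R² = k/(n − 1). For n = 36 this is 8/35 = 0.23 with eight markers and 3/35 = 0.09 with three.

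**The case against.** The best defence is that the conflict is one of labels. The Design section explains its order, so its independent variable can be read as a grouping factor, and comparing markers across risk-change groups is legitimate. The analysis section clearly points to benefit as the target. The subgroup and significant-modification wording shows that a categorised benefit was intended, so what is missing is a cut-off. Association has no direction either: an odds ratio from 60% versus 30% is (0.6/0.4) / (0.3/0.7) = 3.5 whichever variable is the outcome. In simulated logistic models with one binary covariate, the two directions gave practically identical tests. And in a prospective cohort, once benefit is defined, its probability given a marker can be counted directly.

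Much of this stands. The descriptive comparison is sound, the tests of H1 survive, and direction alone costs nothing in error rate. The 5% null rate above comes from linear models and supports only that concession. The counts are of table rows, some of which bundle several markers, and the table gives no timing; baseline status comes from the Design section.

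The main point is not answered. Prediction does have a direction, and the written roles are the wrong way round for it. An intended grouping with no scale, cut-off or visit is not an outcome that can be fitted. The step that would recover predicted benefit from the stated direction is not described. A single sentence in the analysis section naming the outcome would help, but it would leave the Design section and the table saying the opposite.

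**Conclusion.** The concern holds and should be fixed. The stated variable roles contradict the promised predictive model, and the planned logistic regression has no defined benefit outcome. The damage is confined to the multivariable and predictive step; single-marker associations and the descriptive comparison across risk-change subgroups are unaffected.

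The contradiction rests on the text and table alone. The size of the gap between the two directions rests on assumed marker frequencies, benefit rates and correlations, so those figures illustrate it and do not estimate it for this cohort. The 9 to 15 open outcomes are counted from the document.

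**What to change.** For the multivariable and predictive step, swap the roles in the Design section and the variables table. In the analysis section:

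- Name one cardiovascular risk measure at one visit, fixed in advance, as the dependent variable, and adjust for that measure's baseline value, which is already collected. If a prognostic scale is used, say which one.
- Enter together a small prespecified set of baseline markers as predictors. About 36 patients cannot support all eight rows.
- Analyse the measure on its quantitative scale. If logistic regression is kept, fix the benefit cut-off before the data are seen.
- Report the remaining markers as single-marker associations, and keep the comparison of markers across risk-change subgroups as a descriptive analysis.

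The choice of measure, visit and markers is the sponsor's. The cost is rewording three sections, making those choices early, and being able to call fewer markers independent predictors. No new patients, data or procedures are needed.

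### The main association objective groups a quantitative change in cardiovascular risk into subgroups with no stated number, cut-point or reason, which costs information that about 37 patients cannot spare

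*Combined protocol and SAP*

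**What the plan says.** Four parts of the combined protocol and SAP bear on this.

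- **Specific Objectives, third item:** "Determine the association of the cardiovascular prognosis modification (risk subgroups) with the basal metabolic profile".
- **Design:** of the two variables, the one to stratify on is the risk change: "it will be more convenient to determine and stratify based on the change in cardiovascular risk". The sentence goes on to contrast this with stratifying on the baseline adipose profile.
- **Definition of variables and units of measurement:** the three tabled risk measures (prognostic scales, flow mediated dilatation, carotid intima media thickness) are each typed "Quantitative discontinuous".
- **Definition of the processing plan and presentation of the information:** the inferential methods are "difference of averages, correlation, strength of association and relative risk", followed by "multivariate logistic regression analysis to evaluate independent associations". The variables most associated with risk modification then form a predictive model of the greatest benefit.

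The plan does not say how many subgroups there are, where the cuts lie, or why a quantitative change should be grouped. Nor does it say which variables enter the correlation or which variable is the logistic outcome.

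**The concern.** The third objective carries the study's hypothesis. Grouping a quantitative change treats all patients on one side of a cut as alike and near-identical patients on either side of it as different. A real association between an adipose marker and benefit is then more likely to be missed. Measurement error near a cut moves patients between groups. Because the cuts are not stated, they could be chosen after the data are seen, and the result could depend on that choice. The loss does not depend on which variable is called dependent, since grouping weakens the association in either direction.

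**Working it through.** **1. The plan's sample size.** Inputs from the Design section: z = 1.96, p = 0.20, d = 0.13.

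n = z²p(1−p)/d² = 3.8416 × 0.16 / 0.0169 = 0.6147 / 0.0169 = 36.37.

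The printed 36.3 is reproduced (truncated). I round up to 37. The comparison group, "10 non-obese patients undergoing non-bariatric surgery", is additional. This formula sets the precision of one proportion and gives no power for the third objective.

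**2. Information kept after grouping.** Assumptions, not in the documents: the risk change is normal and its association with the marker is linear. For two groups with share q on one side of the cut,

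E = φ(z_q)² / [q(1−q)].

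For several ordered groups, E is the sum over groups of (φ(a) − φ(b))² / group share, where a and b are the group's limits. For equal thirds the limits are ±0.431 and φ = 0.3636, so E = 2 × 0.3636² / (1/3) = 0.793.

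| Grouping | E | Loss | 37 patients are worth |
|---|---|---|---|
| Two groups, 50/50 | 0.3989²/0.25 = 0.637 | 36% | 23.6 |
| Two groups, 70/30 | 0.3477²/0.21 = 0.576 | 42% | 21.3 |
| Two groups, 80/20 | 0.2800²/0.16 = 0.490 | 51% | 18.1 |
| Equal thirds | 0.793 | 21% | 29.3 |
| Equal quarters | 0.861 | 14% | 31.8 |
| Equal fifths | 0.897 | 10% | 33.2 |

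A 90/10 split would lose 66%.

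**3. Power at n = 37.** Simulation of a bivariate normal marker and risk change, with a two-sided 5% t-test of the correlation. Ordered groups are scored for trend. The 20/80 split is 7 against 30 patients. The true correlations are assumed.

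| True correlation | Ungrouped | Median split | 20/80 | Thirds |
|---|---|---|---|---|
| 0.40 | 71% | 50% | 38% | 60% |
| 0.45 | 82% | 61% | 46% | 71% |

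The value 0.45 is a natural reference: by Fisher's z, 37 patients give 80% power for tanh[(1.96 + 0.8416)/√34] = 0.447.

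**4. Dichotomous markers.** The tissue markers are tabled as present or absent. For a marker split 50/50 with latent correlation 0.45, power is about 61% with the change ungrouped and about 43% after a median split. Power starts lower, but grouping still reduces it.

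**5. Misclassification at a median split.** If the reliability of the measured change is R, the share of patients in the wrong group is arccos(√R)/π: 22% at R = 0.6 and 15% at R = 0.8. Both values of R are assumptions.

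**The case against.** Four objections have force, and each limits what may be claimed.

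- **Convenience.** A reader might infer that the change is grouped for convenience. The text does not say so. The convenience argument explains why risk change, and not the adipose profile, is the stratifying variable. No reason for grouping is given at all.
- **A fixed loss of 36–51%.** A reader might take this range as a property of the plan. It holds only for two groups cut between 50/50 and 20/80. The 0.20 in the sample size is the expected prevalence of an unnamed event, not a cut. With three to five equal groups the loss is 21% down to 10%.
- **Logistic regression as proof of a cut.** A reader might infer that logistic regression shows the risk change is dichotomised. The plan labels the adipose profile as dependent, and the tissue markers are dichotomous, so on those labels they could be the logistic outcomes. The predictive model of greatest benefit points the other way. The text is ambiguous.
- **Correlation is listed.** It could use the ungrouped change, so the loss need not reach every analysis. The hypotheses and the general objective do not mention subgroups either.

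The central point remains. The third objective names subgroups and the Design section commits to stratifying on the change. Correlation is bivariate and cannot supply adjusted associations. Every grouping in the table loses information, and the plan names no gain in return.

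**Conclusion.** The concern holds in conditional form. The plan groups a quantitative risk change for its main association, in about 37 patients, without giving the number of groups, the cuts or a reason. Under normality and linearity the loss is about 36% (median split) to 51% (20/80) with two groups, and about 21% with equal thirds. For a continuous marker at a true correlation of 0.45, power drops from about 82% to 61%, 46% and 71%. These figures show what is at stake and are not a prediction, because the documents do not fix the grouping, the correlation or the distribution. The defect is an avoidable loss of power and an open choice of cut-point. It does not make the study invalid.

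**What to change.** Amend the third objective, the Design section and the processing plan as follows.

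- Make the main analysis a linear regression of follow-up risk on each baseline adipose marker, adjusted for the baseline value of the same risk measure. Report slopes with 95% confidence intervals. The baseline term is needed; without it the regression does not address change.
- Build the predictive profile on the same quantitative outcome.
- Keep risk subgroups for descriptive tables or figures only. If the sponsor still wants them in an inferential analysis, the number of groups and the cuts should be fixed and justified beforehand.

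The text should also name the risk measure and which of the 3, 6 and 9 month visits the regression uses. A grouped analysis would need the same decision, so this adds no burden of its own.

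No extra patients, visits or measurements are required. The downside is small: results are slopes rather than odds ratios, and residuals must be checked.
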